Given the promising outcomes, leaders from around the world have implemented the treatment algorithm in their local clinical practices with similar results. We have therefore launched the National Cardiogenic Shock Initiative (NCSI). The aim of the NCSI is to bring together experienced centers across the nation who are experts in mechanical reperfusion therapies and have a large experience with the use of mechanical circulatory support devices to systematize care in AMICS. Our goal is to dramatically decrease the duration patients remain in cardiogenic shock and attempt to decrease total usage and duration of vasopressors and inotropic agents. We aim to further demonstrate that rapid delivery of mechanical circulatory support will improve hemodynamics, reverse the spiraling neuro-hormonal cascade associated with cardiogenic shock, allowing clinicians to decrease use of vasopressors and inotropic agents and ultimately improve survival.

Healthcare systems that have agreed to adopt the NCSI treatment algorithm are being asked to participate in this prospective registry so that patient outcomes can be analyzed (see Appendix 2). Participating investigators will be asked to voluntarily provide data from patients completing the treatment algorithm to be included in the NCSI Registry.

Research Procedures

After a patient has been treated according to the NCSI treatment algorithm at the discretion of their physician (see Appendix 1), they will be approached prior to discharge and asked to participate in NCSI registry, including obtaining permission to allowing coordinators to conduct a 1-month and 1-year follow-up. This data collection can occur via follow up phone call, electronic chart review, or any other method that complies with the site's SOPs. If the patient is discharged prior to obtaining consent, consent form and explanation of the study can be mailed to the patient for their signature and return. If more than one (1) year has passed, all data may be obtained retrospectively.

If consent is provided, then the following data will be collected (see case report form - Appendix 3):

Retrospective Data (from their medical records)

- Medical history
- Admission characteristics
- Procedure dates and times
- Procedure characteristics
- Diagnostic values
- Post-procedure information

Prospective Data (from follow-up) (see Appendix 5 and Appendix 6)

- Mortality at 1 month from AMICS
- Mortality at 12 months from AMICS

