This is not a treatment study. This is a single-arm prospective registry that captures data generated during procedures which are considered standard of care using FDA-approved technology. There are no risks other than breach of confidentiality. To mitigate this risk, patient identifiers are not being captured, and all data will be stored in a secure REDCap database

(please see below). There are no benefits in participation other than the scientific knowledge gained, and the only alternative to participation is not participating.

Data Management

Data collected by the participating sites will be stored and managed in a secure REDCap study database hosted through the Henry Ford Health System Department of Public Health Sciences in Detroit, Michigan. REDCap (Research Electronic Data Capture) is a secure, web-based application designed to support data capture for research studies. A specific database was created solely for NCSI in September 2017. The REDCap database that was custom-built for this study includes only the specific data fields that pertain to the data points being collected in the study, which are present on the case report form (CRF) (see Appendix 3).

For patients who present to affiliated hospitals with AMICGS but are excluded from entry into the registry, a Patient Exclusion Form will be sent to track the reasons for exclusion (see Appendix 4).

The CRFs and Patient Exclusion Forms from an individual site will be transmitted to the lead site, Henry Ford Hospital, via secure email and accessed only on hospital-approved, password-protected computers and stored on a password-protected and encrypted OneDrive system by Microsoft. Access to the OneDrive system and the REDCap database will be managed at the lead site by the NCSI coordinator and the investigators of the study via hospital-approved, password-protected computers inside locked offices in Henry Ford Hospital.

Access to Patient Information

The following will have access to the de-identified patient medical information, and any necessary research contracts and Data Use Agreements will be completed for each participating site.

Henry Ford Hospital – Detroit, Michigan:

- The NCSI team:
 - PI
 - Co-Investigator
 - NCSI Coordinator
 - Research Nurse
 - Research Assistant
 - Data Coordinator
- Statistician, based at Henry Ford Hospital

Analysis and Publication of Data

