** QUALITY MEASURES **

- Impella Pre-PCI
- Door to Support Time < 90 minutes
- Establish TIMI III Flow
- Right Heart Cath
- Wean off Vasopressors & Inotropes
- Maintain CPO >0.6 Watts
- Improve survival to discharge to >80%

NATIONAL CARDIOGENIC SHOCK INITIATIVE

[contact]

www.henryford.com/cardiogenicshock

NationalCSI - Algorithm - v1.5 - 11/2017

APPENDIX 2

Adoption of the NCSI Treatment Algorithm & Joining the NCSI

Adoption to the NCSI treatment algorithm is completely voluntary. Deviation from the treatment algorithm can occur without consultation of the primary investigators at the discretion of the primary operator. All AMICS patients, including those with treatment algorithm deviation, can be included in the NCSI registry as there is no formal, nationally accepted or standardized protocol or treatment algorithm for treatment of AMICS. Operators and hospitals are encouraged to review the pilot study data and treatment algorithm to determine if they wish to adopt the NCSI treatment algorithm as their standard of care for the treatment of AMICS.

Multi-hospital collaboration is considered a cornerstone to the success of the NCSI. We are reaching out nationally and encouraging hospitals to work together to collect data and demonstrate the success of regional shock protocols and/or treatment algorithms. Hospitals joining the NCSI group voluntarily agree to share data, post-discharge, including demographics, procedural characteristics and outcomes as detailed in the case report form. Data is de-identified and HIPAA-compliant. Data generated from the index procedure admission to discharge (or death, if prior to discharge) will be collected retrospectively and de-identified. Prior to discharge, surviving patients will be asked to consent to the collection of data at 30 days and 1 year post-index procedure. This data collection can occur via follow up phone call, electronic chart review, or any other method that complies with the site's SOPs.

To formally join and affiliate with NCSI, we request the minimum following requirements of the interested hospitals:

1. Implantation of >10 Impella per year (for any indication)

2. Adoption of the NCSI treatment algorithm as standard of care for patients who present with AMICS
3. Identification of a local Primary Investigator (PI) to coordinate data collection

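### Research Procedures and the Exclusion Form leave out a survivor who refuses follow-up consent, while Appendix 2 keeps that patient's index-admission data

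*Protocol*

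**What the plan says.** **Research Procedures.** Treated patients are invited into the registry as a whole: "they will be approached prior to discharge and asked to participate in NCSI registry". For a patient who has already gone home, the "consent form and explanation of the study can be mailed to the patient for their signature and return". Then comes the condition "If consent is provided, then the following data will be collected". The list under it covers the retrospective index record (history, admission, procedure, diagnostic and post-procedure items) as well as mortality at 1 and 12 months. One further sentence reads "If more than one (1) year has passed, all data may be obtained retrospectively"; it does not say whether consent is still needed.

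**Appendix 2.** "Data generated from the index procedure admission to discharge (or death, if prior to discharge) will be collected retrospectively and de-identified". No consent condition is attached. Consent comes next and is narrower: "surviving patients will be asked to consent to the collection of data at 30 days and 1 year post-index procedure".

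**Appendix 4, Patient Exclusion Form.** A single yes among the exclusion items excludes the patient, and one item is refusal to sign for the one-month and one-year follow-up. The Registry Exclusion Criteria in the protocol body have no such item.

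**The metric affected.** Discharge survival is the first of the tracked Quality Metrics. The algorithm sheet in Appendix 1 sets the aim "Improve survival to discharge to >80" per cent. The case report form (Appendix 3) asks about survival to discharge and, for those who died, the main cause of death.

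**The concern.** Under Appendix 2, consent controls only what happens after discharge. Under Research Procedures and the Exclusion Form, it controls whether the patient is in the registry at all. These are different inclusion rules, and the choice between them is not neutral for discharge survival. A patient who can be asked about 30-day and 1-year follow-up shortly before going home is nearly always a patient who will be discharged alive. Excluding those who refuse, while deaths are entered, takes patients mainly out of the numerator's side of the ratio and lowers the rate.

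The loss may also be hard to repair at analysis. The Exclusion Form carries site, date, age, gender and race but no discharge status, so an analysis plan could count the refusers without knowing how they fared.

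**Working it through.** The conflict is one of wording, and the protocol has no sample-size or precision calculation to reproduce. The texts are set side by side first, then the possible size is illustrated.

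**1. Three kinds of patient under each text**

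| Patient | Appendix 2 | Research Procedures | Exclusion Form |
|---|---|---|---|
| Survivor who refuses follow-up consent | index data in | out | out |
| Discharged alive, mailed form not returned | index data in | no consent, so out, unless the one-year sentence admits the data | no item applies |
| Died before being approached | index data in | no route stated, unless the one-year sentence or another consent route applies | no item applies |

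Only the first row is a plain contradiction. The other two are unclear.

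**2. Inputs for the illustration**
- N = 500. The protocol plans to approach about 500 patients; here this is taken as 500 eligible treated patients (assumption).
- True discharge survival of 76%, the figure the protocol reports for its 41-patient pilot, used only as an assumed value. It gives S = 380 alive and D = 120 dead.
- r, the share of survivors lost through refusal: 5, 10 and 20%, all assumed.
- All deaths entered, as Appendix 2 and the case report form imply.

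**3. Refusing survivors removed, deaths kept**

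Observed survival = S(1 − r) / [S(1 − r) + D]

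- r = 5%: 361/481 = 75.1%
- r = 10%: 342/462 = 74.0%
- r = 20%: 304/424 = 71.7%

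The shifts from 76.0% are 0.9, 2.0 and 4.3 points.

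**4. Comparison with sampling error**

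The 95% half-width is 1.96 × √(0.76 × 0.24/500) = 3.7 points. The shift equals this at r of about 17.8%.

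**5. If some refusers die in hospital**

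Take 40 refusers, a fraction d of whom die before discharge. Observed survival = [380 − 40(1 − d)] / 460.

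- d = 0: 340/460 = 73.9%
- d = 10%: 344/460 = 74.8%
- d = 24%: 349.6/460 = 76.0%

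The downward bias disappears only if refusers die as often as everyone else. That is unlikely for people asked near discharge.

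**6. Bounds when refusers' status is unknown**

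With 40 refusers of whom 10% died, 380 − 36 = 344 known survivors remain. Counting all 40 as dead gives 344/500 = 68.8%. Counting all as alive gives 384/500 = 76.8%. The interval is 40/500 = 8.0 points wide and contains the assumed 76.0%.

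**The case against.** Several points on the other side are sound.

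*The numbers are assumed and may be small.* The protocol gives no refusal rate. At 5 to 10% of survivors lost, the shift is 0.9 to 2.0 points, inside the 3.7-point half-width. The protocol attaches no hypothesis test or decision rule to discharge survival, and the 80% figure is a quality aim. The direction is also against the registry's own hope. All of this stands and limits the severity. The bias is nonetheless systematic, and a larger registry would not reduce it.

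*Refusers can be counted.* Data Management has Exclusion Forms sent to the lead site to track reasons for exclusion, and refusal has its own box. A reader might infer that nobody could tell how many patients were left out. For refusers handled through the form, that is not so. Only their discharge status is missing.

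*Deaths.* A reader might infer from Research Procedures that patients who die cannot consent, so that deaths are lost and survival is inflated. The documents do not support this. Appendix 2 expressly covers death before discharge, the case report form has fields for it, the one-year sentence may offer a route, and a waiver or proxy provision may lie in consent pages not available here.

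*Non-returned mailed forms.* The one-year sentence may admit these patients too, and the Exclusion Form speaks only of refusal. This case is unclear and should not be called a contradiction.

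*The general participation wording.* The statement that "the only alternative to participation is not participating" comes from the risk and benefit text. It is weak evidence of a data-entry rule, and nothing here rests on it.

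*Which rule is right.* Making Appendix 2 govern outright would presume an ethics basis for using the admission data of people who declined. The documents do not show one.

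**Conclusion.** The contradiction holds for one group: survivors who refuse follow-up consent. Appendix 2 enters their index-admission data, while Research Procedures and the Exclusion Form keep them out, the latter through an item missing from the Registry Exclusion Criteria. If deaths are entered and refusers are not, discharge survival is biased downward unless refusers die in hospital as often as other patients. Under the assumed 500 patients and 76% survival, the shift is about 1 point at 5% of survivors lost, 2 points at 10% and 4 points at 20%. It exceeds sampling error only near 18%.

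The handling of unreturned forms and of deaths before approach is unclear, and no direction of bias should be claimed from it. The point should be fixed because it affects who is counted in the first listed metric and because discharge status not collected may be unrecoverable. The documents do not show that the registry's results are already distorted.

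**What to change.** State one rule for index-admission data and align Research Procedures, the Registry Exclusion Criteria, Appendix 2 and the Exclusion Form with it. Say whether the one-year retrospective sentence requires consent, and how unreturned forms and deaths before approach are handled.

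- *Where the ethics approval allows de-identified index data without consent:* let consent control only the 30-day and 1-year follow-up, and remove refusal of follow-up from the Exclusion Form.
- *Where it does not:* keep refusers out and add a de-identified discharge-status item to the Exclusion Form, if permitted. If it is not permitted, report the numbers of refusers, unreturned forms and deaths before approach. Give bounds on discharge survival, counting every patient of unknown status first as dead and then as alive.

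The cost is an amendment to the protocol and forms, reissued to about 75 sites, with matching database changes. Where bounds are needed, the stated uncertainty widens; in the 40-refuser example the bounds span 8.0 points before sampling error is added.

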From this data, the following Quality Metrics will be tracked:

- Discharge survival
- Duration of shock-to-support times

- Use of Impella Support pre-PCI
- Use of right heart catheter for hemodynamic monitoring
- Attainment of TIMI III flow post reperfusion
- Attainment of Cardiac power > 0.6 watts after completion of therapy
- Reduction or elimination of vasopressors and inotropic agents.

Population and Eligibility Criteria

Due to the heterogeneous cohort of patients who present with AMICS, we have defined a specific subset of patients from whom outcomes are to be collected. Approximately 500 adult patients will be approached to participate in the registry at approximately 75 sites in the United States. The duration of hospital participation in this research study is anticipated to be approximately 3 years.

Registry Inclusion Criteria

1. Symptoms of acute myocardial infarction (AMI) with ECG and/or biomarker evidence of S-T elevation myocardial infarction (STEMI) or non-S-T elevation myocardial infarction (NSTEMI)
2. Cardiogenic shock is defined as the presence of at least two of the following:
 - a. Hypotension (systolic blood pressure ≤ 90 mm Hg, or inotropes/vasopressors to maintain systolic blood pressure ≥ 90 mmHg)
 - b. Signs of end organ hypoperfusion (cool extremities, oliguria or anuria, or elevated lactate levels)
 - c. Hemodynamic criteria represented by a cardiac index of < 2.2 L/min/m² or a cardiac power output ≤ 0.6 watts.

3. Patient is supported with an Impella
4. Patient undergoes PCI

Registry Exclusion Criteria

1. Evidence of Anoxic Brain Injury
2. Unwitnessed out of hospital cardiac arrest or any cardiac arrest in which return of spontaneous circulation (ROSC) is not achieved within 30 minutes
3. IABP placed prior to Impella
4. Septic, anaphylactic, hemorrhagic, and neurologic causes of shock
5. Non-ischemic causes of shock/hypotension (pulmonary embolism, pneumothorax, myocarditis, tamponade, etc.)
6. Active bleeding for which mechanical circulatory support is contraindicated
7. Recent major surgery for which mechanical circulatory support is contraindicated
8. Mechanical complications of AMI (acute ventricular septal defect (VSD) or acute papillary muscle rupture)
9. Known left ventricular thrombus for which mechanical circulatory support is contraindicated
10. Mechanical aortic prosthetic valve
11. Contraindication to intravenous systemic anticoagulation

Risks/Benefits of and Alternatives to Patient Participation

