Support was weaned according to: PA Sat Echo RHC Hemodynamics
 Other: _____

Total hospital duration (Days): _____

Left Ventricle Ejection Fraction (Pre-Impella): _____ (Prior to discharge): _____

DID THE PATIENT SURVIVE THE INDEX PROCEDURE? Yes No N/A

Was the patient transferred to VAD/Transplant Center Yes No N/A

 If "Yes", DID THE PATIENT SURVIVE TO TRANSFER? Yes No N/A

Did the patient have any additional support devices implanted post-index procedure? Yes No N/A

 If "Yes", which device was used: _____

DID THE PATIENT SURVIVE TO DISCHARGE? Yes No N/A

Was the patient discharged to hospice? Yes No N/A

Did the patient experience any significant Impella-related complications?

NO Vascular Complications Hemolysis

OTHER – Please explain: _____

Did the patient require any blood transfusions? No Yes – # of transfusions: _____

Was any external form of vascular bypass performed to provide lower extremity perfusion during Impella (i.e. antegrade access, "up and over" perfusion catheter, etc.)?

No Yes – Please Explain: _____

Please provide a brief description of the patient's hospital course (including significant complications and discharge circumstances):

Please Explain: _____

If the patient did not survive, please indicate the major cause of death (fatal bleeding, anoxic brain injury, worsening cardiogenic shock, patient/family wishes?)

Please Explain: _____

Cardiac Medications on Discharge (name only): _____

- END OF FORM -

APPENDIX 4
Patient Exclusion Form

National Cardiogenic Shock Initiative

PATIENT EXCLUSION FORM

(Version 2.0)

Please complete and email this form via [SECURE] email to: [contact].
Please email/call if there are any questions or concerns.

Hospital: _____

Hospital - City, State: _____

Physician: _____

Date: _____

Age: _____

Gender: Male Female Other

Race: White Black Hispanic Other

Patients will be excluded if there is at least one NO response to the inclusion criteria or at least one YES response to the exclusion criteria.

INCLUSION CRITERIA:

YES NO

- | | | |
|--------------------------|--------------------------|---|
|  |  | ACUTE MI: Symptoms with ECG and/or biomarker evidence of STEMI or NSTEMI |
|  |  | CARDIOGENIC SHOCK: Defined by the presence of at least two of the following: |

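### Exclusions 6, 7, 9, 10 and 11 can only remove patients already treated with Impella and PCI, without a pre-insertion time anchor or structured outcomes for those removed

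*Protocol*

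**What the plan says.** Under Population and Eligibility Criteria, inclusion 3 reads "Patient is supported with an Impella" and inclusion 4 requires PCI. Three of the exclusions are worded as bars to mechanical support: item 6, "Active bleeding for which mechanical circulatory support is contraindicated"; item 7, on recent major surgery, with the same qualifier; and item 9, "Known left ventricular thrombus for which mechanical circulatory support is contraindicated". Item 10 is a mechanical aortic prosthesis. Item 11 is "Contraindication to intravenous systemic anticoagulation".

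Entry comes after the procedure. Research Procedures says "After a patient has been treated according to the NCSI treatment algorithm at the discretion of their physician", and then "they will be approached prior to discharge and asked to participate in NCSI registry". Appendix 2 adds: "Data generated from the index procedure admission to discharge (or death, if prior to discharge) will be collected retrospectively and de-identified".

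Three other parts of the protocol bear on the same items:

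- **Appendix 1, algorithm sheet.** It lists all five conditions ahead of cath-lab activation and device placement. Bleeding, surgery and thrombus appear without the contraindication qualifier.
- **Appendix 4, Patient Exclusion Form.** One YES to any exclusion removes the patient. Items 6, 7 and 9 again lack the qualifier, and item 11 is absent. The form has ticks for Impella and PCI, the reasons for exclusion and a free-text Notes area, but no field for survival or complications.
- **Appendix 2.** It allows all patients with infarct-related shock into the registry, including those whose treatment departed from the algorithm.

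Survival to discharge and the question "Did the patient experience any significant Impella-related complications" are on the Case Report Form (Appendix 3), which is completed only for entered patients.

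**The concern.** These five items are screening rules for the period before implant, reused as registry exclusions after it. That would do little harm if status were fixed at a defined time before insertion. It is not. The person completing the form can know how the hospital stay went, and the protocol does not say when or by whom the condition is judged.

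Item 6 shows the difficulty best. The operator implanted the device, so support was presumably thought acceptable at that moment. The site later decides whether bleeding was present and, under the main text, whether it contraindicated support. The Exclusion Form asks only about active bleeding, with no time attached. Item 11 has a similar problem, because a bar to anticoagulation can arise during support.

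Discharge survival is the first Quality Metric listed, and the algorithm sheet sets a target above 80% for it. If who stays in can depend on what happened, that figure and the complication rate lose a clear denominator. No analysis plan could repair this later, because outcomes of the removed patients are not collected in a structured field.

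**Working it through.** **1. Whom can the five items affect?** Cross implant status with the presence of a listed condition, for patients who meet all other criteria:

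| Impella and PCI | Condition present | Entered without items 6, 7, 9–11 | Entered with them |
|---|---|---|---|
| No | No | No | No |
| No | Yes | No | No |
| Yes | No | Yes | Yes |
| Yes | Yes | Yes | **No** |

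Only the last row changes. The sole effect of these items on the analysed set is to remove treated patients.

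**2. How exposed is each item to later events?** Items 7, 9 and 10 (recent surgery, known thrombus, mechanical valve) are mainly facts from before the procedure, and the hospital course does not create them. Items 6 and 11 can arise after insertion. The link of item 11 to the device comes from Appendix 1, which places anticoagulation before insertion.

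**3. How large could the effect be?** The protocol reports neither how many patients are removed nor how they fare, so there is no stated figure to reproduce and what follows is illustration. Let p be survival among those kept, s survival among those removed, and f the share of treated patients removed. Then

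survival in all treated = p(1 − f) + s·f, and the shift = f(p − s).

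With p = 76% (the pilot figure in the protocol's background) and s = 40% (assumed):

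- f = 2%: 76 × 0.98 + 40 × 0.02 = 75.28%
- f = 5%: 76 × 0.95 + 40 × 0.05 = 74.20%
- f = 8%: 76 × 0.92 + 40 × 0.08 = 73.12%

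The same formula for complications, with 15% in those kept and 50% in those removed (both assumed), gives 15.70%, 16.75% and 17.80%.

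**4. Wider range.** Take p = 76% or 80%, f from 2% to 15% and s from 25% to 75%. The smallest shift is 0.02 × (76 − 75) = 0.02 points. The largest is 0.15 × (80 − 25) = 8.25 points. With s = 75% the shift is at most 0.15 × (80 − 75) = 0.75 points.

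**5. Scale.** With 500 patients, the 95% half-width at 76% is 1.96 × √(0.76 × 0.24 / 500) = 3.7 points. The shifts in step 3 (0.7 to 2.9 points) are smaller than that, but they are systematic and a larger registry would not reduce them.

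**The case against.** The strongest reply is that this is ordinary. In any registry that enters patients after treatment, every exclusion acts only on treated patients, and exclusions 1 to 5 and 8 do so too. The protocol says that it has chosen a specific subset, and patients without a contraindication to support are a legitimate target population. This stands: the table in step 1 does not by itself show a defect, and it does not follow that the five exclusions should be void.

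Second, a reader might infer that a patient who bleeds on support is meant to be reclassified out. The documents do not say so. The algorithm sheet lists bleeding before cath-lab activation, and the Case Report Form asks about transfusions and offers fatal bleeding as a cause of death, so it expects some patients who bleed to remain. What stands is narrower: the criteria and the Exclusion Form do not rule such a reclassification out.

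Third, it would be too strong to say that the removed patients leave no trace. The Exclusion Form shows that they had Impella and PCI and why they were excluded, and Notes could hold more. They can be counted, except under item 11, which has no tick. Their outcomes still have no dedicated field.

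Fourth, complications are a Case Report Form item and not a listed Quality Metric, and reporting an additional analysis set is usual material for an analysis plan. Both are fair. The analysis, however, needs data that the present forms do not collect.

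**Conclusion.** The point holds in a limited form. The text establishes four things: these items can remove only treated patients; their timing is not fixed relative to insertion, which matters most for items 6 and 11; the criteria, the algorithm sheet, the Exclusion Form and Appendix 2 disagree on wording and on whether such patients belong in the registry; and outcomes of those removed are not captured in a structured way.

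A reader might go further and conclude that the survival and complication figures are biased in the device's favour. The documents do not support that as a fact. Worse outcomes in the removed patients are plausible, but neither their number nor their course is reported, and if they survived about as often as the rest the effect would be negligible. On the assumptions shown, the survival shift is 0.7 to 2.9 points in the main illustration and from almost none to about 8 points over the wider range. This merits correction because it is cheap to fix now and cannot be repaired at analysis.

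**What to change.** 1. In Registry Exclusion Criteria and Appendix 4, state that items 6, 7, 9, 10 and 11 are judged only on status documented before Impella insertion, and that bleeding or a bar to anticoagulation arising on support never excludes a patient from the registry.
2. Reconcile the eligibility section, the algorithm sheet in Appendix 1, the Exclusion Form and Appendix 2: use one wording for items 6, 7 and 9, add item 11 to the form, and say whether a patient implanted despite a listed condition counts as an includable algorithm deviation or as an exclusion.
3. For any patient who had Impella and PCI but is excluded under these items, record discharge status and Impella-related complications.
4. Report discharge survival and complications for the defined subset, and again for all patients who received Impella and PCI.

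The cost is a few form fields, an edit to the criteria, and possibly a slightly less favourable figure. The change concerns who is recorded and analysed; it sets no rule on who should receive the device.
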